13.0 Study Timelines*

13.1 *Describe the anticipated duration needed to enroll all study subjects.*

Response: All data will be collected in two years of a time window.

13.2 *Describe the duration of an individual subject's participation in the study. Include length of study visits, and overall study follow-up time.*

Response: Maximum of three hours will be used to collect the data

13.3 *Describe the estimated duration for the investigators to complete this study (i.e. all data is collected and all analyses have been completed).*

Response: We expect to collect and analyze the data within three years.

14.0 Setting

14.1 *Describe all facilities/sites where you will be conducting research procedures. Include a description of the security and privacy of the facilities (e.g. locked facility, limited access, privacy barriers). Facility, department, and type of room are relevant. Do not abbreviate facility names.*

NOTE: Examples of acceptable response may be: "A classroom setting in the Department of Psychology equipped with a computer with relevant survey administration software," "The angiogram suite at Buffalo General Medical Center, a fully accredited tertiary care institution within New York State with badge access," or, "Community Center meeting hall."

Response: [name] laboratories are located in 809 Furnas and 115 Kimball. The laboratories are equipped with a Vicon motion capture system, Delsys sEMG system, smart insole, Kinect cameras, and Bertec Force plate instrumented

treadmill. A computer station can control Vicon, Delsys, Bertec system, and smart insole all together simultaneously.

14.2 For research conducted outside of UB and its affiliates, describe:

- *Site-specific regulations or customs affecting the research*
- *Local scientific and ethical review structure*

NOTE: This question is referring to UB affiliated research taking place outside UB, i.e. research conducted in the community, school-based research, international research, etc. It is not referring to multi-site research. UB affiliated institutions include Kaleida Health, ECMC, and Roswell Park Cancer Institute.

Response:

N/A: This study is not conducted outside of UB or its affiliates.

15.0 Community-Based Participatory Research

15.1 Describe involvement of the community in the design and conduct of the research.

NOTE: Community-Based Participatory Research (CBPR) is a collaborative approach to research that equitably involves all partners in the research process and recognizes the unique strengths that each brings. CBPR begins with a research topic of importance to the community, has the aim of combining knowledge with action and achieving social change to improve health outcomes and eliminate health disparities.

Response:

N/A: This study does not utilize CBPR.

15.2 Describe the composition and involvement of a community advisory board.

Response:

N/A: This study does not have a community advisory board.

16.0 Resources and Qualifications

*16.1 Describe the qualifications (e.g., education, training, experience, expertise, or certifications) of the Principal Investigator **and** staff to perform the research. When applicable describe their knowledge of the local study sites, culture, and society. Provide enough information to convince the IRB that you have qualified staff for the proposed research.*

NOTE: If you specify a person by name, a change to that person will require prior approval by the IRB. If you specify a person by role (e.g., coordinator, research assistant, co-investigator, or pharmacist), a change to that person will not usually require prior approval by the IRB, provided that the person meets the qualifications described to fulfill their roles.

Response:

The principal investigator has various experiences to collect biomechanical data of healthy individuals, Parkinson's disease, and cerebellar ataxia patients. PI has been published experiments that include motion capture systems and sEMG systems. All researchers who are working with PI will finish CITI program training to establish a basic knowledge of human subjects research.

Describe other resources available to conduct the research.

16.2 *Describe the time and effort that the Principal Investigator and research staff will devote to conducting and completing the research.*

NOTE: Examples include the percentage of Full Time Equivalents (FTE), hours per week. The question will elicit whether there are appropriate resources to conduct the research.

Response: We estimate that the PI will devote 20% of their time to the study. Other PIs will devote 5s% of their time to the study. The research assistance will devote 30% of their time to the study.

16.3 *Describe the availability of medical or psychological resources that subjects might need as a result of anticipated consequences of the human research, if applicable.*

NOTE: One example includes: on-call availability of a counselor or psychologist for a study that screens subjects for depression.

Response: There will be a licensed physical therapist ([name] or other physical therapist) when we conduct this study.

16.4 *Describe your process to ensure that all persons assisting with the research are adequately informed about the protocol, the research procedures, and their duties and functions.*

Response: PI will train all personnel who will conduct human subject studies. Their role will be assigned and informed about the protocol, procedures, and duties. Before starting this study, all staff members will run a dry-run test to practice their knowledge.

17.0 Other Approvals

17.1 *Describe any approvals that will be obtained prior to commencing the research (e.g., school, external site, funding agency, laboratory, radiation safety, or biosafety).*

Response:

N/A: This study does not require any other approvals.

18.0 Provisions to Protect the Privacy Interests of Subjects

18.1 *Describe how you will protect subjects' privacy interests during the course of this research.*

NOTE: Privacy refers to an individual's right to control access to him or herself. Privacy applies to the person. Confidentiality refers to how data collected about individuals for the research will be protected by the researcher from release. Confidentiality applies to the data.

Examples of appropriate responses include: "participant only meets with a study coordinator in a classroom setting where no one can overhear", or "the participant is reminded that they are free to refuse to answer any questions that they do not feel comfortable answering."

Response: Participants will be assigned an unidentifiable code when analyzing the data. During the study, the participant can ask questions anytime or stop the study.

18.2 *Indicate how the research team is permitted to access any sources of information about the subjects.*

*NOTE: Examples of appropriate responses include: school permission for review of records, consent of the subject, HIPAA waiver. This question **does apply** to records reviews.*

Response: All data collection occurs after the subject has signed the consent form.

19.0 Data Management and Analysis*

19.1 *Describe the data analysis plan, including any statistical procedures. This section applies to both quantitative and qualitative analysis.*

Response: The collected motion capture data will be labeled and filtered with a 4th order Butterworth filter. All sEMG data will be post-processed by bandwidth filter, enveloped, smoothed, and scaled. To define the beginning and the end of each repetition the speed of the markers is used as a threshold. The data will be time-scaled and averaged over different trials.

The analyses for CP subjects are carried out separately. Descriptive statistics will be obtained to compare the randomized groups on baseline factors including pre-existing chronic conditions, underlying disease, demographics, and other potential confounders. When the numeric data are not normally distributed based on graphic inspection (e.g., normal quantile plots), we will consider the Box-Cox transformation. For numeric data, a mixed-effects model will be constructed, where

major factors include the effect of time within each day, the effect of feedback, the effect of the day as well as the effect of the random assignment. Major statistics to obtain will be improvement measures between baseline and the end of treatment. An appropriate covariance structure will be considered reflecting the correlations within subjects. Various contrasts will be tested to see an improvement by the major factors. Some other covariates such as demographic and other subjects characteristics can be included in the models if a significant difference is shown. Residual plots will be examined to check the normality of the residual. If not normally distributed, we will consider simpler nonparametric methods that compare specific factor combinations in a form of various contrasts. For categorical data, we will construct a similar model to the numeric data, except that we will use an appropriate link function based on the generalized linear model. The covariance structures will be incorporated into the analysis using a generalized structural equation modeling strategy. For this pilot study, we do not consider controlling family-wise Type I error as the purpose of the study is to see the viability of the treatment and potentially support the bigger clinical trials in the future.

19.2 If applicable, provide a power analysis.

NOTE: This may not apply to certain types of studies, including chart/records reviews, survey studies, or observational studies. This question is asked to elicit whether the investigator has an adequate sample size to achieve the study objectives and justify a conclusion.

Response: A goal of this study is to test the feasibility and efficacy of the proposed intervention in the improvement of gait characteristics. Currently, no previous study is available to have the treatments both resistance training and sensory feedback. For CP subjects, we will have a sample size of 20 (10 each group), which requires an effect size of 0.5 to have a power of 80% with the size of the test 0.05 in the two-group comparison with 6 repeated measures under the assumption of compound symmetry with auto-correlation 0.1.

19.3 Describe any procedures that will be used for quality control of collected data.

Response: The post-processed data will be visually investigated whether all the procedures were properly applied. Outliers will be also detected during this investigation.

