3.0 Scientific Endpoints*

2.1 Describe the scientific endpoint(s), the main result or occurrence under study.

*NOTE: Scientific endpoints are outcomes defined before the study begins to determine whether the objectives of the study have been met and to draw conclusions from the data. Include primary and secondary endpoints. Some example endpoints are: reduction of symptoms, improvement in quality of life, or survival. Your response should **not** be a date.*

Response: The two primary outcome measures will be the motion and the muscle activation data of the lower body during walking. Motion trajectory will be used to detect the changes in the kinematics and sEMG data will present the muscle activation of the participants. Ground reaction force, center of pressure, and center of mass will be evaluated with the instrumented insole and treadmill. Before the first and after the last training, participants will be evaluated for functional gait assessment, 6-min-walk, leg strength using dynamometer, international physical activity questionnaire (short form), usability questionnaire, and Modified Ashworth test by a physical therapist. This will show the kinematic and kinetic changes of the participant after the training.

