5.0 Study Design*

5.1 *Describe and explain the study design (e.g. case-control, cross-sectional, ethnographic, experimental, interventional, longitudinal, observational).*

Response: The experiment protocol involves a maximum of ten sessions and will take two or three hours for each session. Baseline data will be collected before the first session for both overground and treadmill walking. During this session, the sound level will be adjusted based on the feedback received from the users. The researcher will ask the comfortable sound level to the participant before starting the experiment. Training will be conducted on the treadmill with the cable-actuated device for about 20 minutes. When the cables were removed, participants walked on the treadmill for 4 minutes during the post-training session. During training and post-training, participants will be exposed to feedback while walking on the treadmill. After treadmill walking, CP participants will be asked to take a ten-minute break and then practice overground walking for two minutes with auditory feedback (type A) and without it (type B). Effects of 3 different types of

auditory feedback will be explored namely, rhythmic sounds, movement sonification, and sound notifying erroneous gait. Group A participants will be further divided into groups depending on the type of auditory feedback that will be provided. Participants will participate in a maximum of 10 sessions, two or three times a week. Before the first and after the last training, participants will be evaluated for functional gait assessment, 6-min-walk, leg strength using a dynamometer, international physical activity questionnaire (short form), usability questionnaire, and Modified Ashworth test by a physical therapist.

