of training with a cable-actuated robot will be provided. The device will augment 15% of their own body weight. While they are walking with the device, auditory feedback will be provided for the participants who are assigned to the auditory group. The auditory and non-auditory groups will be randomly assigned. Furthermore, one of the 3 different types of auditory feedback will be randomly assigned to participants from the feedback group. A break of 5 minutes will be provided after 10 minutes of walking with the device. After the robotic training is completed, the device will be taken off and the participant will walk without the device to monitor the immediate retention of the training. After every 10 minutes, the researcher will ask the participant questions as per the Borg exertion scale to check the fatigue of the participant. After finishing the treadmill session, participants will take a 10-minute break and walk 4 minutes with (or without auditory feedback) on the floor. The participant will repeat overground walking for a total of three sets. There will be a total of ten training sessions, two or three sessions a week and each session will last for a maximum of 3 hours. In addition, pre and post-training visits are required to evaluate functional gait assessment, 6-min-walk, leg strength using a dynamometer, international physical activity questionnaire (short form), usability questionnaire, and Modified Ashworth test by a physical therapist.

12.2 Describe what data will be collected.

NOTE: For studies with multiple data collection points or long-term follow up, consider the addition of a schedule or table in your response.

Response:

- We will schedule the participants to visit the lab. We will make a table when the participants are available.
- *EMG data from the muscles*
- *Vicon motion capture data*
- *Photo and Video of the test*
- *IMU sensor data*
- *Smart insole data*
- *Ground reaction force*

12.3 List any instruments or measurement tools used to collect data (e.g. questionnaire, interview guide, validated instrument, data collection form).

Include copies of these documents with your submission.

Response: Vicon motion capture system, Delsys Trigno sEMG system, and Bertec Force plate instrumented treadmill, Smart Insole

12.4 Describe any source records that will be used to collect data about subjects (e.g. school records, electronic medical records).

Response: N/A

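### The randomised auditory v non-auditory contrast rests on improvement from baseline, with no stated adjustment for the outcome's own baseline and a data-driven rule for other covariates

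*Combined protocol and SAP*

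**What the plan says.** Section 19.1 plans a mixed-effects model for numeric data. Its major factors are time within the day, feedback, and "the effect of the day as well as the effect of the random assignment". On the target of estimation it says "Major statistics to obtain will be improvement measures between baseline and the end of treatment", and on testing, "Various contrasts will be tested to see an improvement by the major factors".

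The same section uses baseline in one other way: "Descriptive statistics will be obtained to compare the randomized groups on baseline factors". It then gives a rule for covariates: "Some other covariates such as demographic and other subjects characteristics can be included in the models if a significant difference is shown". It does not say which difference is meant, at what level, or for which characteristics.

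Baseline values will exist. Section 5.1 says of the gait data: "Baseline data will be collected before the first session for both overground and treadmill walking". Section 3.0 says of the functional measures: "Before the first and after the last training, participants will be evaluated for functional gait assessment, 6-min-walk, leg strength using dynamometer". Section 12.1 confirms this: "In addition, pre and post-training visits are required to evaluate functional gait assessment, 6-min-walk, leg strength using a dynamometer". Section 12.1 also says that the auditory and non-auditory groups are assigned at random, and mentions no stratification.

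No section says that an outcome's baseline is a covariate, or that baseline is a response with the same mean in both groups.

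**The concern.** There are two separate gaps, both in the between-group comparison.

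The first is baseline handling. A change score fixes the baseline coefficient at 1, whatever the correlation between baseline and end values. When that correlation is moderate or low, this adds noise. It also over-corrects any imbalance that randomisation happens to produce, to the disadvantage of the group that started higher. Imbalance is a real prospect with 10 v 10, no stated stratification, and eligibility (Section 8.1) that spans ages 18 to 65 and walking with or without assistive devices.

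The second is the covariate rule. The significant difference could be a baseline difference between groups or an association with the outcome. Either way, the covariate set is settled after the data are seen, in a plan that already allows various contrasts without family-wise error control.

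Section 19.2 names efficacy as well as feasibility as a goal, and Section 19.1 hopes to support larger trials. The between-group estimate and its interval are therefore likely to be reused.

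**Working it through.** The plan gives no figure on this point to reproduce. The power statement in Section 19.2 mentions neither a change score nor baseline adjustment. Its correlation of 0.1 is not stated to cover baseline, so it is not used here.

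**Inputs.** 10 participants per group (Section 19.2). Assumptions: one baseline and one end value per person, baseline SD = 1, end SD = 1 unless varied, complete data, and a baseline-to-end correlation r taken over a range because the documents give none.

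**Formulas.** The multiplier for a difference of two means is 1/10 + 1/10 = 0.2.

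- Change score: SE = sqrt(0.2 × 2(1 − r)), 18 df, t = 2.101.
- Adjusted for baseline: SE = sqrt(0.2 × (1 − r²) × 17/16), 17 df, t = 2.110. The factor 17/16 is the average price of estimating the slope.
- Example, r = 0.5: change sqrt(0.2 × 1.00) = 0.447; adjusted sqrt(0.2 × 0.75 × 1.0625) = 0.399.
- Equivalent number = 20 × (adjusted SE / change SE)².
- Shift of the change-score estimate, given an observed baseline difference d: −(1 − r)d, shown for d = 0.5 SD. The adjusted estimate shifts by 0 on average.

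| r | SE change | SE adjusted | 95% half-width, change v adjusted | 20 analysed by change carry the information of about | Shift at d = 0.5 SD |
|---|---|---|---|---|---|
| 0.3 | 0.53 | 0.44 | 1.11 v 0.93 | 14 | 0.35 |
| 0.5 | 0.45 | 0.40 | 0.94 v 0.84 | 16 | 0.25 |
| 0.7 | 0.35 | 0.33 | 0.73 v 0.69 | 18 | 0.15 |
| 0.8 | 0.283 | 0.277 | 0.59 v 0.58 | 19 | 0.10 |
| 0.9 | 0.200 | 0.201 | 0.42 v 0.42 | 20 | 0.05 |

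A simulation of 60,000 trials at each r agreed with these SEs to within about 0.003.

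**Break-even, equal SDs.** Setting 2(1 − r) = (1 − r²) × 17/16 gives 1 + r = 32/17, so r = 0.88.

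**Unequal SDs.** Let the end SD be 1.3 times the baseline SD. At r = 0.7:

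- change: sqrt(0.2 × (1 + 1.69 − 1.82)) = 0.417
- adjusted: sqrt(0.2 × 1.69 × 0.51 × 17/16) = 0.428

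Equating the two variances gives 1.7956r² − 2.6r + 0.8944 = 0, with roots 0.563 and 0.885. Between those values the change score has the slightly smaller SE.

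**Worst case for adjustment.** Apart from the slope price, the adjusted variance is the smallest that any baseline coefficient can give, including a coefficient of 1. The SE ratio therefore cannot exceed sqrt(17/16) = 1.031, whatever r or the SD ratio.

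**Size of chance imbalance.** The baseline difference between two groups of 10 has SD sqrt(0.2) = 0.45 outcome SD. It exceeds 0.5 SD in either direction in about 26% of randomisations, under normality.

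The covariate rule is not quantified, because the text does not say what is tested.

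**The case against.** The strongest reply is that the plan specifies a mixed model, not a two-point change-score test. Improvement could be a contrast within that model. If baseline is a response with a common mean across groups, the contrast is close to an adjusted analysis. If the groups have separate baseline means and the data are complete, it is the change-score contrast. The text does not say which. This part stands: the figures above apply to the second reading only, and a reader who infers that the plan has ruled out adjustment goes further than Section 19.1 does.

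The size of the benefit is also unknown. By the figures above it is about 2% in SE at r = 0.8 and nil at 0.9, and the 0.88 break-even needs equal SDs. This stands too, but the loss from adjusting is bounded at about 3%, while the possible gain is larger.

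The change is not purely mechanical either. Section 3.0 names motion and muscle activation data as primary without reducing them to single values, and baseline is taken both overground and on the treadmill. The matching baseline must therefore be named outcome by outcome. The argument also does not carry over directly to the categorical models or the nonparametric fallback. The fix is limited accordingly.

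Pilot status carries some weight, since Section 19.1 speaks of viability. However, Section 19.2 also names efficacy and plans a two-group test at 0.05. Finally, the covariate wording is permissive, but a permissive rule triggered by significance still lets the data decide.

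**Conclusion.** The point holds as one of precision and pre-specification, and the plan should be changed. Section 19.1 makes improvement from baseline the major statistic for contrasts that include the random assignment. It does not say how the collected baseline enters, and it lets a significance result decide other covariates.

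On a two-point change-score reading with equal SDs, the avoidable loss in SE is material at r of 0.3 to 0.5, small at 0.7, and negligible at 0.8 to 0.9. Since r is an assumption, no single loss can be stated. The covariate problem does not depend on r.

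Three stronger readings are tempting and are not supported:

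- That the change score biases the comparison. Under randomisation it does not. The shift shown above is conditional on an observed imbalance and averages out over randomisations.
- That the trial will lose the equivalent of several participants. That needs both the change-score reading and a low or moderate r, and the documents fix neither.
- That the plan tests baseline differences between groups to choose covariates. It may, but the text does not say so, and it calls the baseline comparison descriptive.

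**What to change.** For the auditory v non-auditory contrast on each numeric outcome, state one of two analyses in Section 19.1: the outcome's own baseline, measured under the same walking condition (overground or treadmill) where it is a gait outcome, as a covariate; or a mixed model with baseline as a response and equal baseline means in the two groups. Report the adjusted end-of-treatment difference with its 95% CI.

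Delete the condition that admits covariates on a significant difference, and keep baseline comparisons descriptive. Name any further prognostic covariates in advance, and keep them few. If uninformative, one beyond the baseline raises the worst-case SE penalty to sqrt(17/15) = 1.065, and two raise it to sqrt(17/14) = 1.102.

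Keep within-person change for objective 1 (benefit of training), where it answers the question asked.

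The cost is wording, plus the decision on which baseline matches each outcome. No new data are needed. With the baseline covariate alone, the statistical price is one degree of freedom per outcome and at most about 3% in SE.

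### The 80% power in section 19.2 does not follow from its own two-group inputs, and the effect-size metric it depends on is not defined

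*Combined protocol and SAP*

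**What the plan says.** Section 19.2 is the only sample-size justification. It opens with the aim: "A goal of this study is to test the feasibility and efficacy of the proposed intervention". It then gives the size, "we will have a sample size of 20 (10 each group"), and the operating characteristics: "which requires an effect size of 0.5 to have a power of 80% with the size of the test 0.05 in the two-group comparison". The same sentence fixes the number of measures per participant and their correlation: "with 6 repeated measures under the assumption of compound symmetry with auto-correlation 0.1".

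It does not say whether 0.5 is a standardised mean difference or Cohen's f, which SD scales it, whether the test is one- or two-sided, which test or software was used, or which outcome and contrast the figure applies to.

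Section 19.1 does not supply the contrast. It says "Major statistics to obtain will be improvement measures between baseline and the end of treatment" within a mixed-effects model, and then "Various contrasts will be tested to see an improvement by the major factors". It also states that "the purpose of the study is to see the viability of the treatment and potentially support the bigger clinical trials in the future".

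**The concern.** Section 19.2 gives every number needed for a two-group comparison of repeated measures except the definition of the effect size and the sidedness. The candidates for those two can be listed and tried. If none returns 80%, supplying the missing definition will not be enough, because the 80% itself would also have to change.

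What is at stake is what 20 participants can show. Section 19.2 puts efficacy beside feasibility as a goal. A reader who takes 0.5 as half an SD will think the trial better powered than it is; a reader who takes it as Cohen's f will think it worse powered than it is. The figure would do most harm if carried into the planning of the larger trials that section 19.1 has in view.

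**Working it through.** **Inputs, all from section 19.2.** n = 10 per group; effect 0.5; α = 0.05; m = 6 measures; compound symmetry with ρ = 0.1. No dropout allowance is given, so none is applied.

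**Attempt to reproduce 80%: 0.5 in SDs of a single measurement (σ = 1), averaged over the six measures.**

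- Variance of a participant's mean: (1 + (m − 1)ρ)/m = (1 + 5 × 0.1)/6 = 0.25.
- Noncentrality: 0.5/√(0.25 × 2/10) = 0.5/0.2236 = 2.236, with 20 − 2 = 18 df for the t test.

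| Test | Power at 0.5 | Difference detectable with 80% power |
|---|---|---|
| Two-sided t | 56.2% | 0.66 SD |
| Two-sided normal | 60.9% | 0.63 SD |
| One-sided t | 69.4% | 0.58 SD |
| One-sided normal | 72.3% | 0.56 SD |

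A simulation of 200,000 trials gave 56.1% (two-sided t) and 69.3% (one-sided t). Using 118 df instead of 18 raises the t results only to 60% and 72%. Reaching 80% at 0.5 SD would take 16 to 17 per group two-sided, or 13 to 14 one-sided.

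**0.5 as Cohen's f for the between-group effect.** λ = f²·N·m/(1 + (m − 1)ρ) = 0.25 × 20 × 6/1.5 = 20. With F(1, 18), power is 98.8%. Power of 80% needs f of about 0.33.

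**0.5 in SDs of the six-measure mean.** Noncentrality is 0.5 × √5 = 1.118, and power is 19% to 30% over the same four tests. This reading is unlikely, because the six measures and the 0.1 would then not enter the calculation.

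**Near-matches that alter the stated design.**

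- AR(1) with 0.1 in place of compound symmetry: variance of the mean 0.1968. Two-sided power is 66.4% (t) or 71.2% (normal); one-sided it is 78.2% or 80.9%.
- One group of 10 under compound symmetry: noncentrality 0.5/√(0.25/10) = 3.162, 9 df, two-sided t, power 80.3%. This is not a two-group comparison.
- Independent measures (ρ = 0): 78.2% with a two-sided normal test. This contradicts the stated 0.1.
- Rounding: an effect of 0.549 gives 79.1% with a one-sided normal test but 64% with a two-sided t.

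**Why the contrast matters.** Suppose one baseline and six later measures, all correlated 0.1, with the same 0.5 SD difference. Adjusting for baseline gives variance 0.25 − 0.01 = 0.24 and power of 58% to 74%. Subtracting baseline gives variance 0.25 + 1 − 0.2 = 1.05 and power of 18% to 29%. Section 19.1 names improvement from baseline as the major statistic but does not say which of these is meant.

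**The case against.** The strongest objection is that this shows missing detail and not an error. The readings run from 19% to 99%, on both sides of 80%, and the software output that might define the metric is not in the document. It is true that the direction of the discrepancy is unknown and that the source of the 80% cannot be identified.

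Two specific routes to 80% deserve weight. First, the plan's own phrase joins compound symmetry to auto-correlation, and the hypothesis in section 2.2 is directional, so a one-sided AR(1) calculation is a plausible origin. If so, the paragraph names the wrong structure and omits the sidedness, and it still needs correcting.

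Second, a single-df group-by-time contrast keeps two groups, six measures and compound symmetry. Taking f = 0.25 (0.5 read as 2f), λ = 0.0625 × 120/0.9 = 8.33, and power is 77.9% with F(1, 18) or 81.5% with F(1, 90). This shows that the list of readings cannot be called exhaustive. But it describes group differences that average to zero over time, for example a 1.0 SD shift between the first and second halves of the measures. That is not what a two-group comparison with an effect of 0.5 ordinarily means, and the text names no such contrast.

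It is also fair to say that on the effect-size scale the gap is smaller (0.5 against 0.56 to 0.66 SD), and that a pilot does not stand or fall on its power statement.

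**Conclusion.** The point holds. With two groups of 10, six measures and compound symmetry at 0.1, an average group difference of 0.5 single-measurement SD gives 56% to 72% power, and a between-group Cohen's f of 0.5 gives about 99%. Neither is 80%. The conclusion rests on a time-averaged two-group comparison, complete data and the stated correlation.

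The established fault is that the figure is not reproducible from its inputs. It is not established that the study is underpowered, since that depends on a metric the plan does not define. The correction should be made, but its consequences are limited: the study is a pilot, and its size, data collection and analysis are unaffected.

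**What to change.** Rewrite the power paragraph in section 19.2 to state the effect-size definition and the SD behind it, the sidedness, the test, a single correlation structure and the contrast. Then give the power that those choices yield.

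- **If the metric is single-measurement SDs with a two-sided t test**, for example: *With 10 participants per group, two-sided α of 0.05, six measures and compound symmetry with correlation 0.1, power is about 56% for a group difference, averaged over the six measures, of 0.5 SD of a single measurement; the difference detectable with 80% power is about 0.66 SD.*
- **If it is Cohen's f between groups**: say so, and give about 99%, with 80% power at f of about 0.33.
- **If another calculation was used** (AR(1), one-sided, a single group, or a time contrast): describe that calculation and remove the wording that contradicts it. The 80% may stand if the description then supports it.
- **If the figure is meant for the baseline-to-end improvement in section 19.1**: define that contrast and any baseline adjustment first, then compute the power for it.

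The cost is one paragraph of text. The number of participants, data collection and analysis stay as they are.
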